- Participants with serum creatinine $> 1.5 \text{ mg/dL}$ will be excluded from the study, and serum creatinine will be evaluated at each clinic visit.
- Should the serum creatinine increase to $> 2.0 \text{ mg/dL}$ but $\leq 3 \text{ mg/dL}$, rIL-2 will be interrupted. rIL-2 may be resumed at 3.5 million units twice daily when creatinine falls to $< 1.5 \text{ mg/dL}$. If the creatinine remains $\leq 1.5 \text{ mg/dL}$ on the reduced dose of 3.5 million units twice daily, this dose will be continued until the end of the study.
- If serum creatinine rises again to $> 1.5 \text{ mg/dL}$ while on the reduced dose of 3.5 million units twice daily, rIL-2 will be interrupted until creatinine falls to

< 1.5 mg/dL and then rIL2 may be resumed at 2 million units twice daily. If serum creatinine then remains below 1.5 mg/dL, this dose will be continued until the end of the study. If serum creatinine rises again to >1.5 mg/dL while on the reduced dose of 2 million units twice daily, rIL2 will be permanently discontinued.

- Should serum creatinine rise to > 3.0 mg/dL , rIL-2 will be discontinued permanently

I.6.1.5. Risk Mitigation Strategy for Malignancies

To minimize the risk of emergent or recurrent malignancies, subjects with a history of or active cancer will be excluded, and a review of interval diagnoses or medical events and a full or targeted physical exam will be performed at each visit. Additionally, concomitant immunosuppressive medications will be prohibited during the study.

I.6.1.6. Risk Mitigation Strategy for Viral Reactivation

The risk mitigation strategy for viral reactivation includes:

- Volunteers with evidence of active hepatitis B or C infection will not be enrolled in the study.
- Participants who develop herpes zoster will be required to discontinue treatment until completion of treatment and resolution of symptoms.
- Participants who develop a recurrence of herpes zoster or multidermatomal involvement will be required to discontinue study treatment permanently.
- Participants who develop a detectable HBV DNA while on study will require permanent study discontinuation.

I.6.1.7. Risk Mitigation Strategy for Blood Sample Collection and Intavenous Infusion

The most common risks of blood sample collection are pain at the puncture site, bruising, and a feeling of lightheadedness. To minimize these risks, blood draws will be performed by trained personnel, and will be performed in a secure environment with access to first aid equipment, bandages, and trained healthcare professionals.

I.7. Adequacy of Protection against Risks

I.7.1. Recruitment and Informed Consent

Before the initiation of any study procedures, subjects will be informed about the study and asked to sign an IRB approved informed consent/HIPAA document. Subjects will be consented in a private exam room. Subjects will be given time to read the consent, ask questions and consider the risks and/or benefits to participation in this research study prior to obtaining their signature. All subjects enrolled in the study will be given a copy of their signed and dated informed consent document. This consenting process will be done by trained research staff at the Case Clinical Trials Unit.

I.7.2. Protections against Specific Study-related Risks

An extensive risk mitigation strategy has been implemented to address risks derived specifically from the study treatments and procedures. Details of the risk minimization strategy for each risk category are provided above. All study-related activities will be conducted in private areas to protect patient confidentiality.

I.8. Potential Benefits of the Proposed Research to Human Subjects and Others

Participants in this trial are not expected to derive a direct benefit from their participation. If this trial provides proof of concept for the notion that rIL-2 decreases the size of the persistent HIV reservoir in peripheral blood, the results could offer the starting point for the implementation of a therapeutic strategy to cure or induce ART-free remission of HIV infection and that could result in a tangible clinical benefit to persons living with HIV/AIDS, including those directly involved in the study.

I.9. Importance of the Knowledge to Be Gained

As there is great community and scientific interest in developing strategies to allow cure or remission of HIV infection, confirmation of a significant effect of rIL-2 administration on indices of HIV persistence will be important to both enhance understanding of mechanisms of persistence as well as to provide a therapeutic strategy that could contribute to HIV eradication or remission.

I.10. Data and Safety Monitoring Plan

The two PIs, Drs. [name] and [name], both experienced HIV clinical trialists, will review all adverse events, determine their relationship to study procedures, and generate reports to the IRB as needed. The data manager will prepare data reports every four months, and inconsistencies in data elements will be resolved by review of primary sources, interview with research personnel, and general consensus among study team members. The protocol statistician will be responsible for preparing the overall data reports, and for alerting the team to trends in adverse event frequency or data discrepancies. Trial safety will be monitored by an SMC.

I.11. ClinicalTrials.gov Requirements

When regulatory approval is secured, this study will be registered with ClinicalTrials.gov. Results information (including adverse events) will be reported no later than 1 year after the primary completion date per Food and Drug Administration Amendments Act (FDAAA) requirements (http://grants.nih.gov/ClinicalTrials_fdaaa/steps.htm).

I.12. Inclusion of Women and Minorities

Both men and women will be included in the trial. Minorities, including Spanish-speaking persons, will be eligible to enroll in the trial, and a Spanish language consent will be available for them.

I.13. Inclusion of Children

Children ages 18 to 21 will be included in this study.

J. PUBLICATION OF RESEARCH FINDINGS

Publication of the results of this trial will be decided by consensus of the study team.

K. BIOHAZARD CONTAINMENT

As the transmission of HIV and other blood-borne pathogens can occur through contact with contaminated needles, blood, and blood products, appropriate blood and secretion precautions will be employed by all personnel in the drawing of blood and shipping and handling of all specimens for this study, as currently recommended by the Centers for Disease Control and Prevention and the National Institutes of Health.

All dangerous goods materials, including diagnostic specimens and infectious substances, will be transported using packaging mandated by CFR 42 Part 72, as per the International Air Transport Association (IATA) Dangerous Goods Regulations.

L. REFERENCES

1. Gulick RM. Treatment with indinavir, zidovudine, and lamivudine in adults with human immunodeficiency virus infection and prior antiretroviral therapy. *N Engl J Med.* 1997;337:734-9.

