The progression of thyroid dysfunction during rIL-2 treatment is variable, but it is thought to involve an initial period of thyroid stimulation akin to autoimmune thyroiditis, which is usually undetected, followed by variable degrees of hypothyroidism (50, 55, 57). The mechanisms of these effects on the thyroid are incompletely understood. It has been proposed that IL-2-mediated induction of proinflammatory cytokine production may trigger the initial autoimmune thyroiditis (48, 50, 51). This notion is supported by the finding of increased lymphocyte infiltration of the thyroid, with features suggestive of autoimmune thyroiditis, during rIL-2 treatment (58, 59). In this model, the initial thyroiditis may result from enhancement of class II expression and presentation of autoantigens by thyrocytes due to increased local release of proinflammatory cytokines by thyroid-infiltrating mononuclear cells (48, 51). The clinical course of rIL-2-induced thyroid dysfunction has not been comprehensively described, but at least in some cases, there is spontaneous resolution of the thyroid abnormalities. In a closely monitored study of a single cycle of rIL-2 administered to 20 euthyroid HIV-infected participants, there was a rapid concomitant rise in TSH, T3, T4, and free T4 within the first three days of treatment, with return of all indices to baseline after approximately 14 days (55). The need for thyroid hormone replacement for rIL-2-induced hypothyroidism has been variable and inconsistently reported. In 3 out of 7 participants who developed hypothyroidism in a trial of rIL-2 given with LAK cells for malignant diseases, thyroid function tests returned to normal while these participants were not receiving thyroid replacement, but the authors indicate that they could not ascertain the course of thyroid dysfunction for other participants (49). In a similar study of cancer patients, thyroid function tests returned to the normal range in the absence of thyroid replacement therapy approximately 6 months after treatment among 4 of the 7 participants with rIL-2-induced hypothyroidism. The remaining 3 participants received levothyroxine and also had normal thyroid tests 6 months after rIL-2 treatment, but it is unclear if thyroid replacement had been discontinued by that time (48). In a study including 49 HIV-infected participants randomized to either low (1.5 MIU

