SC BID) or high (7.5 MIU SC BID) dose rIL-2, 2 of the 5 participants who developed hypothyroidism did not receive thyroid replacement therapy, but the duration of thyroid replacement and the follow-up results of thyroid function tests were not reported (33).

Risk factors for thyroid dysfunction during rIL-2 treatment include female sex, pre-existing thyroid dysfunction, large cumulative doses of rIL-2, and importantly, the presence of anti-thyroid antibodies (49, 50, 57). The association of IL-2 thyroid dysfunction with the presence of anti-thyroid antibodies has not been accurately quantified, but it has been observed in multiple reported studies (48, 49, 52). In one study including 34 cancer patients, antithyroid antibodies were present in none of the 27 participants who remained euthyroid during treatment, but were present in 5 out of the 7 (71%) participants who developed hypothyroidism (49, 52). Therefore, in this study, participants will be screened for the presence of anti-thyroid antibodies (in addition to routine thyroid function testing) both at study entry and before each rIL-2 cycle. Participants who have abnormal thyroid function tests or elevated levels of antithyroid antibodies at screening will be excluded. Participants who develop abnormal thyroid function tests or antithyroid antibodies at any time during study participation will be required to discontinue study treatment permanently.

Patients may experience mental status changes when taking rIL-2, including irritability, insomnia, confusion, or depression. Mental status changes due solely to rIL-2 are generally reversible when drug administration is discontinued. However, alterations in mental status may continue for several days before recovery begins.

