3. HIV-1 infection, documented by and FDA-approved ELISA, EIA, or rapid antibody detection method, and confirmed by a second approved antibody-based test or by a positive approved HIV RNA detection assay.
4. CD4+ T cell count ≥ 350 cells/mm 3 .
5. HIV-1 RNA < 50 copies/mL obtained within 60 days prior to study entry performed with an FDA-approved HIV-1 RNA assay.
6. Adequate venous access and no other contraindications for leukapheresis.
7. Absolute neutrophil count (ANC) ≥ 1500 /mm 3 .
8. Hemoglobin level >10 g/dL.
9. Platelet count $\geq 100,000$ /mm 3 .

² Accelevir, data on file

10. Serum creatinine ≤ 1.5 mg/dL
11. AST and ALT < 2.5 times the upper limit of normal
12. TSH, T3, and T4 levels within the normal range of the processing laboratory.
13. Anti-thyrosine peroxidase (TPO) antibodies within the normal range of the processing laboratory.
14. Willing to comply with study-mandated evaluations; including not changing antiretroviral regimen (unless medically indicated) during the study period.
15. All participants must have received HAART, and had viral loads below the limit of quantification of the assay for at least 1 year. Participants who had intermittent isolated episodes of detectable low-level viremia < 500 copies RNA/mL flanked by viral loads below the limit of quantification of the assay will remain eligible.
16. On a stable combination antiretroviral regimen (no changes to treatment within 4 weeks of enrollment) including at least 3 medications and willing to continue on current antiretroviral therapy for the duration of the study, unless otherwise medically indicated.

C.4. EXCLUSION CRITERIA

1. Childbearing potential for female participants. For the purposes of this study, a woman is considered to be of childbearing potential if she is not postmenarchial, has not had a documented surgical sterilization procedure, has an intact uterus and at least 1 ovary, and has had a spontaneous menstrual period in the last 2 years.
2. Acute or chronic hepatitis C infection, defined as a positive plasma HCV RNA using any FDA-approved qualitative or quantitative test in a participant with a positive HCV antibody (HCV RNA testing is not required in participants with a negative HCV antibody). Participants who have completed a course of a direct-acting antiviral agent for hepatitis C and have a confirmed plasma HCV RNA level below the limit of detection of the assay 12 weeks or longer after completion of therapy will be eligible.

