All modifications to antiretroviral medications post-entry will be recorded on the CRF. If the modification includes discontinuation of antiretrovirals, the rules for treatment discontinuation (section F.3) must be followed.

D.3.5. Laboratory Evaluations

All clinical laboratory results will be stored as part of the source document. Only emerging (i.e. not present before or at the time of entry) laboratory values grade 2 or higher must be recorded on the CRF.

D.3.5.1. Clinical Laboratory Tests

All clinical labs will be processed in the CLIA-certified clinical laboratory of University Hospitals Cleveland Medical Center. Clinical laboratories include:

- CBC will include hemoglobin, hematocrit, white cell count with differential and platelet count. This test will be submitted and results obtained in real time.
- Metabolic panel will include at least glucose, BUN, creatinine, sodium, potassium, chloride, bicarbonate, total and direct bilirubin, AST, ALT, and alkaline phosphatase.

This test will be submitted and results obtained in real time.

- HIV-1 RNA testing will be done using an FDA-approved method with a lower limit of detection of 50 copies/mL or lower. This test will be submitted in real time, but the turnaround time is approximately 3 days.
- HBsAg with reflex HBV DNA, and HCV Ab with reflex HCV RNA will be performed using FDA-approved kits as needed to determine eligibility. These tests will be submitted in real time. Results will be obtained, however, prior to study entry.
- Thyroid function tests will include TSH, T4, and T3 serum levels.

D.3.5.2. Research Evaluations

Specimens for immunologic monitoring, virologic testing, and storage for deferred assays will be processed, stored, and distributed by [name] laboratory as needed. Immunogenicity testing for antibodies against rIL-2 will be done in batched serum using standard methods for both binding and neutralizing activity. These methods will be validated in [name] laboratory before testing of study-derived samples. Refer to the LPC for details on volumes, collections procedures, transport, and processing.

D.4. SPECIMEN COLLECTION, HANDLING, AND PROCESSING

D.4.1. General Specimen Management Guidance

The study site will adhere to the standards of good clinical laboratory practice, DAIDS Laboratory Requirements and site standard operating procedures for proper collection, processing, labeling, transport, and storage of specimens at the local laboratories, as described in

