- If the platelet count drops to $\geq 50,000$ but $\leq 100,000$ /mm 3 while on the reduced dose of 3.5 million units twice daily, rIL2 will be discontinued until the platelet count reaches 100,000/mm 3 and then resumed at a dose of 2 million units twice daily. If the platelet count then remains above 100,000 /mm 3 , this dose will be continued until the end of study. If the platelet count falls again to $\leq 100,000$ /mm 3 while on the reduced 2 million unit twice daily dose, rIL2 will be permanently discontinued.
- Should the platelet count decrease to $< 50,000$ /mm 3 , rIL-2 will be permanently discontinued.

E.1.5. AST and ALT Abnormalities

Participants who develop AST or ALT elevations will be referred for treatment by a qualified healthcare professional. Volunteers with AST or ALT levels $> 2.5 \times$ ULN at screening will be excluded.

- Volunteers with cirrhosis, severe liver disease, or active hepatitis B or C infection will be excluded from the study.
- Should AST or ALT values rise to $> 3 \times$ ULN, rIL-2 will be interrupted. rIL-2 may be resumed at 3.5 million units twice daily when AST or ALT fall to $< 2 \times$ ULN. If AST and ALT values then remain below $3 \times$ ULN, this dose will be continued to the end of study.
- If AST or ALT values rise again to $> 3 \times$ ULN while on the reduced dose of 3.5 million units twice daily, rIL-2 will be interrupted until AST and ALT fall to $< 2 \times$ ULN and then resumed at a dose of 2 million units twice daily. If AST and ALT values then remain below $3 \times$ ULN, this dose will be continued to the end of study. If AST or ALT levels rise again to $> 3 \times$ ULN while on the reduced 2 million unit twice daily dose, rIL2 will be permanently discontinued.
- If ALT values rise again to $> 3 \times$ ULN while the patient is receiving 2 million units twice daily, rIL-2 will be discontinued permanently.
- Should AST or ALT values rise to $> 5 \times$ ULN, rIL2 will be permanently discontinued.

E.1.6. Thyroid Test Abnormalities

Participants who develop thyroid function test (TFT) abnormalities will be referred for treatment by a qualified healthcare professional. Volunteers with abnormal TFTs or levels of anti-thyroid antibodies (anti-Tpo) at screening will be excluded.

- If a participant develops a TSH level $> 3.98 \text{ mIU/L}$, rIL-2 will be permanently discontinued.
- If T3 or T4 levels are outside the normal reference range of the laboratory, rIL-2 will be permanently discontinued.

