 - Lymphoma, primary of brain
 - Progressive multifocal leukoencephalopathy
 - Toxoplasmosis of brain
- Occurrence of herpes zoster reactivation involving more than two dermatomes or visceral involvement including but not limited to viral pneumonia, encephalitis and hepatitis.
- Occurrence of a serious infection that is considered life-threatening or requires inpatient treatment.
- Occurrence of an incident cancer other than a localized basal cell carcinoma of the skin that requires local excision only.
- Requirement for prohibited concomitant medications (see exclusion criteria and section C.6).
- Pregnancy or breastfeeding.
- Deep vein thrombosis or pulmonary embolism.
- Myocardial infarction or other acute coronary syndrome.
- Development of a grade ≥ 3 hypersensitivity reaction, OR a grade 2 hypersensitivity reaction that includes manifestations of angioedema, or suspected or confirmed capillary leak syndrome.
- Development of an ANC < 500 cells/mm³.
- Development of a platelet count $< 50,000$ /mm³.
- Elevation of AST or ALT to > 5 x ULN.
- Serum TSH elevation to ≥ 3.99 mIU/L, abnormal serum T4 or T3 levels, abnormal levels of anti-Tpo antibodies, or symptomatic hypo- or hyperthyroidism.
- Completion of treatment as defined in the protocol.
- Request by participant or his/her healthcare providers to terminate treatment.
- Reasons believed to be clinically significant by the investigators, even if not addressed in the adverse event management section of the protocol.

F.2. PREMATURE STUDY DISCONTINUATION

- Failure by the participant to attend 3 consecutive visits.
- Request by participant or his/her healthcare providers to terminate participation in the study.
- Participant judged by the investigator to be at significant risk of failing to comply with the provisions of the protocol as to cause harm to self or seriously interfere with the validity of the study results.
- At the discretion of the institutional review board (IRB), Office for Human Research Protections (OHRP), FDA, NIAID or investigator.

F.3. TEMPORARY TREATMENT DISCONTINUATION

- Criteria for withholding dose met (refer to section C.5.2 and to Manual of Operations).

G. SAFETY MONITORING

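### For an isolated low TSH, section A.5 requires a permanent stop of rIL-2, while E.1.6, F.1 and I.6.1.4.4 set a TSH stop only for elevated values

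*Combined protocol and SAP*

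**What the plan says.** Section A.5, after explaining why thyroid tests and antibodies are checked in this study, sets a rule: "Participants who develop abnormal thyroid function tests or antithyroid antibodies at any time during study participation will be required to discontinue study treatment permanently".

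Section D.3.5.1 defines the tests: "Thyroid function tests will include TSH, T4, and T3 serum levels". Inclusion criterion 12 (C.3) sets the entry standard: "TSH, T3, and T4 levels within the normal range of the processing laboratory".

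The sections that govern management treat TSH differently from the hormones:

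- **E.1.6** opens with a general instruction: "Participants who develop thyroid function test (TFT) abnormalities will be referred for treatment by a qualified healthcare professional". It then requires a permanent stop for a TSH above 3.98 mIU/L. For the hormones it says: "If T3 or T4 levels are outside the normal reference range of the laboratory, rIL-2 will be permanently discontinued". Raised anti-Tpo and clinical signs or symptoms of hypo- or hyperthyroidism also require a stop.
- **F.1** lists, among the reasons for a permanent stop, "Serum TSH elevation to ≥ 3.99 mIU/L, abnormal serum T4 or T3 levels, abnormal levels of anti-Tpo antibodies", together with symptomatic thyroid disease. A separate item lets the investigators stop treatment for other reasons that they consider clinically significant.
- **I.6.1.4.4** requires a permanent stop at a TSH of 3.99 mIU/L or more, for abnormal T3 or T4, for symptomatic thyroid disease and for raised anti-Tpo.

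**The concern.** A normal range has a lower as well as an upper limit. A.5 makes no distinction of direction, whereas the TSH rules in the other three sections run in one direction only. The same laboratory result can therefore carry a mandatory permanent stop in one section and no TSH-based stop in the others, so two members of staff who each follow the protocol could act differently.

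The stop is permanent, and it reaches the analysis. Section C.2.1 defines the on-treatment set as participants who received all eight cycles, and it plans a model term for the number of cycles received. Which section staff follow would change both. The participant would stay in the primary intent-to-treat analysis, which takes in everyone with at least one dose, but with fewer cycles.

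**Working it through.** There is no figure in the plan to reproduce. The check applies each rule to the same set of cases.

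**Step 1. Is a low TSH an abnormal thyroid function test?** D.3.5.1 names TSH as one of these tests. Criterion 12 judges TSH by the laboratory's normal range, which is two-sided. E.1.6 and I.6.1.4.4 also exclude volunteers with abnormal thyroid function tests at screening. A TSH below the range is therefore abnormal in the protocol's own terms.

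**Step 2. Apply the four sections.**

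| Case | A.5 | E.1.6 | F.1 | I.6.1.4.4 |
|---|---|---|---|---|
| Low TSH; T3, T4 and anti-Tpo normal; no symptoms | Permanent stop | Referral; no stop required | No listed trigger; stop at investigators' discretion | No trigger |
| Low TSH with abnormal T3 or T4, raised anti-Tpo, or thyroid symptoms | Permanent stop | Permanent stop | Permanent stop | Permanent stop |
| TSH 3.99 mIU/L or more | Permanent stop if above the laboratory range | Permanent stop | Permanent stop | Permanent stop |

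Only the first row conflicts whatever the laboratory's limits are.

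**Step 3. Are the two cut-offs different?** No. If TSH is reported to two decimals, the first value above 3.98 is 3.99, so E.1.6 agrees with F.1 and I.6.1.4.4.

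**Step 4. Fixed cut-off against the laboratory range.** Let U be the laboratory's upper limit for TSH, which the documents do not give.

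- U = 3.98: the fixed cut-off and the laboratory range agree.
- U above 3.98: values from 3.99 to U satisfy criterion 12 and are normal under A.5, but meet the stop value in the other three sections.
- U below 3.98: values above U and up to 3.98 are a stop under A.5 only.

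**Step 5. Scale.** One participant is 1/20 = 5% of the planned sample. For thyroid dysfunction of any kind, A.5 gives 2.5% to 11.7% in small studies of subcutaneous rIL-2 in HIV, and a verbal estimate of 10% to 15% for the two large trials. In 20 participants that is 0.025 × 20 = 0.5 to 0.117 × 20 = 2.3, or 0.10 × 20 = 2 to 0.15 × 20 = 3. These figures are context, not a count of isolated low TSH, which the documents do not report.

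**Step 6. How often the rule is applied.** Thyroid tests are listed at screening, at the leukapheresis visit and on day 0 of each of the eight cycles. Seven of these fall after the first exposure (cycles 2 to 8). None is listed at the day 7 visits or the end-of-study visit.

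**The case against.** The strongest reply is that A.5 is background on the agent and should be read as a short summary of the management sections, which agree with one another. That lowers the weight of the point but does not remove it. The sentence is worded as a requirement for participants in this study, and nothing in the protocol says that the later sections take precedence. F.1 also uses different words for TSH (elevation) and for T4 and T3 (abnormal) within one item, so its silence on low TSH cannot be read as shorthand for any abnormality.

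A second reply is that a low TSH is not left without action. This is correct: E.1.6 calls for referral and F.1 permits a discretionary stop. A reader might infer that low TSH triggers nothing outside A.5, and the documents do not support that. Even so, referral or discretion is not a mandatory stop.

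A third reply is that the case will be rare, and this also largely stands. The conflict needs a low TSH with everything else normal. A reader might infer that rIL-2's early stimulation phase makes low TSH likely, because A.5 says of the course of thyroid dysfunction that "it is thought to involve an initial period of thyroid stimulation akin to autoimmune thyroiditis, which is usually undetected". A.5 does not say that TSH falls in that phase. The one closely monitored study it describes found TSH rising together with T3 and T4 within three days, and returning to baseline after about 14 days. Tests on day 0 of the next cycle, 7 to 10 weeks after the previous cycle began, would probably miss a change that short. Nor do the documents say that thyroid toxicity is the most expected reason for stopping.

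Finally, a reader might infer that the fixed cut-off contradicts the entry criterion. That depends on U. Clinical tests are run in one named laboratory, and 3.98 may be its upper limit; the documents neither confirm nor exclude it.

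**Conclusion.** The contradiction is real and narrow. It is confined to a TSH below the laboratory range with normal T3, T4 and anti-Tpo and no symptoms. In that case A.5 mandates a permanent stop that E.1.6, F.1 and I.6.1.4.4 do not require. The conclusion rests only on D.3.5.1 counting TSH as a thyroid function test and on a normal range having a lower limit; no outside figure is needed.

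The number of participants affected is unknown, probably small and possibly zero. The point still merits correction because the stop is irreversible, and because each case shifts 5% of the planned sample out of the on-treatment set and changes a cycle count used in the analysis. The possible mismatch between the fixed cut-off and the entry range is secondary and holds only if the laboratory's upper limit differs from 3.98 mIU/L.

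**What to change.** Reconcile A.5, E.1.6, F.1 and I.6.1.4.4 so that all four give the same instruction for a TSH below the laboratory range when T3, T4, anti-Tpo and symptoms are normal. Which instruction that should be is a clinical decision for the sponsor and investigators, and this review takes no position on it.

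Separately, confirm whether 3.98 mIU/L is the processing laboratory's upper limit. If it is, state so where the cut-off appears. If it is not, reconcile the cut-off with A.5 and criterion 12, so that values between the two limits are handled consistently.

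The cost is an amendment of protocol wording. Sample size, visits and analysis methods are unaffected.
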